4 STUDY DESIGN

4.1 OVERALL DESIGN

This study will use a single-blind, parallel-arm RCT design. Participants will be randomized at a 1:1 ratio to Sleep GOALS intervention (n=20) or an education control group (n=20).

Sleep GOALS: We anticipate Sleep GOALS will be a 16-week intervention. However, the results of Aim 1 will determine the intervention length and core content. We will use a protocol [name] and colleagues developed to adapt TSC to an online format and integrate it with the GOALS lifestyle intervention.^{6,7} Briefly, in-person delivery of TSC has 3 components: 1) delivery of the core content, 2) providing tailored feedback, and 3) providing motivation and support. We will adapt the first component to an online format with 15-to-20-minute informational videos. The participants will view the material at their convenience, with new videos available weekly. The GOALS software will send weekly automated email reminders to review the new session materials. We will use a lifestyle coach to adapt the 2nd and 3rd components. Evaluating patient perspectives on the original GOALS lifestyle intervention found individualized lifestyle coaching, encouragement, and accountability helpful.⁸ The coach will be a master's level student in a health-related program (e.g., physical activity and health promotion, nutrition and dietetics, etc.) with experience in weight-management counseling. As described in Aim 1, the coach will assist with developing Sleep GOALS to familiarize them with the intervention content. However, the coach will complete a 2-day training workshop using a similar training format as the GOALS Lifestyle intervention.⁷ The coach will help participants develop an individualized sleep treatment plan based on their baseline sleep assessment. For example, coaches will encourage participants to document challenges for sleep (e.g., infant sleep, lack of partner support) and identify one treatment strategy they deem feasible to implement each week. The coach will monitor participant progress and engagement weekly to revise the sleep treatment plan, diet, and activity as needed. Coaches will provide personalized feedback and encourage accountability and re-engagement through a secure messaging system in the Sleep GOALS platform.⁷ The PI will randomly check coach-participant communication weekly to ensure intervention fidelity. IF NECESSARY, the PI will meet with the coaches weekly to discuss challenges and participant communication. Lastly, participants will be given a wireless scale for self-monitoring weight and a Fitbit for self-monitoring sleep (daily minutes) and physical activity (daily steps, minutes). The Fitbit dashboard also allows participants to track dietary calories. Participants will receive instructions on how to sync the scale and Fitbit data with the Sleep GOALS platform. Participants will be asked to weigh themselves in light clothing at least once weekly.⁹

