5 STUDY POPULATION

We will enroll 40 primiparous adult individuals between 3 \pm 1 and 6 \pm 1 months postpartum with a body mass index \geq 25 kg/m². We chose this postpartum range because postpartum weight retention during this period is associated with the development of long-term obesity. Additionally, at 3 months postpartum, most infants experience rapid increases in nocturnal sleep; thus, many of our behavioral strategies for improving maternal sleep may be more feasible. Evidence suggests that addressing sleep in infants between 3 and 6 months can prevent longer-lasting sleep problems. Lastly, it is safe for most postpartum individuals to participate in an intervention involving physical activity during this period.

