8.2 ADVERSE EVENTS AND SERIOUS ADVERSE EVENTS

8.2.1 DEFINITION OF ADVERSE EVENTS (AE)

Adverse event means any untoward medical occurrence associated with the use of an intervention in humans, whether or not considered intervention-related (21 CFR 312.32 (a)).

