8.2.3.2 RELATIONSHIP TO STUDY INTERVENTION

All adverse events (AEs) must have their relationship to study intervention assessed by the PI, who examines and evaluates the participant based on temporal relationship and their judgment. The degree of certainty about causality will be graded using the categories below. In a clinical trial, the study product must always be suspect.

- **Related** – The AE is known to occur with the study intervention, there is a reasonable possibility that the study intervention caused the AE, or there is a temporal relationship between the study intervention and the event. Reasonable possibility means that there is evidence to suggest a causal relationship between the study intervention and the AE.
- **Not Related** – There is not a reasonable possibility that the administration of the study intervention caused the event, there is no temporal relationship between the study intervention and event onset, or an alternate etiology has been established.

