8.2.3.3 EXPECTEDNESS

The principal investigator will determine whether an adverse event (AE) is expected or unexpected. An AE will be considered unexpected if the nature, severity, or frequency of the event is not consistent with the risk information previously described for the study intervention.

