8.2.4 TIME PERIOD AND FREQUENCY FOR EVENT ASSESSMENT AND FOLLOW-UP

The occurrence of an adverse event (AE) or serious adverse event (SAE) may come to the attention of study personnel during study visits, community with the lifestyle coach during the intervention, and interviews. We will record all reportable events with start dates occurring any time after informed consent is obtained until 7 days (for non-serious AEs) or 30 days (for SAEs) after the last day of study participation. We will assess and document AEs and SAEs at each study visits, inquiring about the occurrence of AEs and SAEs since the last visit, with a focus on any issues related to sleep, diet, physical activity, or weight loss. We will follow up on all events for outcome information until resolution or stabilization.

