8.3 UNANTICIPATED PROBLEMS

8.3.1 DEFINITION OF UNANTICIPATED PROBLEMS (UP)

The Office for Human Research Protections (OHRP) considers unanticipated problems involving risks to participants or others to include, in general, any incident, experience, or outcome that meets **all** of the following criteria:

- Unexpected in terms of nature, severity, or frequency given (a) the research procedures that are described in the protocol-related documents, such as the Institutional Review Board (IRB)-approved research protocol and informed consent document; and (b) the characteristics of the participant population being studied;
- Related or possibly related to participation in the research (“possibly related” means there is a reasonable possibility that the incident, experience, or outcome may have been caused by the procedures involved in the research); and
- Suggests that the research places participants or others at a greater risk of harm (including physical, psychological, economic, or social harm) than was previously known or recognized.

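### Infant events are neither defined as a safety outcome nor systematically asked about, and the risk list has no entry for the sleep component or the infant

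*Combined protocol and SAP*

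**What the plan says.** All references are to the combined protocol and SAP.

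**Safety inquiry.** Section 8.2.4 provides for adverse events and serious adverse events to be asked about at each visit, "with a focus on any issues related to sleep, diet, physical activity, or weight loss". It adds that events "may come to the attention of study personnel during study visits, community with the lifestyle coach during the intervention, and interviews". Section 8.2.1 defines an adverse event as "any untoward medical occurrence associated with the use of an intervention in humans". Under Section 8.2.3.2 causality is judged by the PI, "who examines and evaluates the participant based on temporal relationship and their judgment".

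**Risk list.** The intervention-related risks in Section 2.3.1 concern physical activity, weight loss and the wrist monitor. The only child-related item is a data-collection risk, the disclosure of neglect or abuse.

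**Where the infant comes in.** Section 4.1 says that "coaches will encourage participants to document challenges for sleep (e.g., infant sleep, lack of partner support" and similar), after which the mother picks a strategy for the week. Section 5 supports the choice of population with the statement "Evidence suggests that addressing sleep in infants between 3 and 6 months can prevent longer-lasting sleep problems". Breastfeeding is a covariate in Sections 3 and 9.4.2 and is not among the three exclusions in Section 5.2.

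**Infant data collected.** Section 1.3 schedules infant feeding and behaviour at baseline and the final assessment, under descriptive characteristics and without restriction by arm. Section 8.1 names an infant sleep questionnaire (BISQ-R Short Form) and an infant feeding questionnaire among the efficacy and covariate assessments.

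**The concern.** The programme can reach a second person. A mother may change how she handles infant sleep, or she may restrict her diet while breastfeeding. The plan counts a possible benefit to infant sleep among its reasons for the age window, but its safety sections do not say how a problem in the infant would be recorded.

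Two things are at stake. First, the pilot could report that no safety concern arose when no standard question about the infant had been put to either arm. Second, any infant events that are reported would not come from comparable sources, because one of the named routes is a coach whom only the Sleep GOALS arm has. A difference between arms, or its absence, could then reflect who was in contact with staff.

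The larger trial would also inherit a risk list that is silent on the sleep component, which Sections 2.2 and 2.3.3 present as the element rarely included in weight-loss programmes.

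**Working it through.** The plan gives no figure on this point, so the main check is to compare its sections.

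1. **Is an infant event an adverse event?** The definition in 8.2.1 refers to humans and so does not exclude the infant. Section 8.2.3.2 evaluates the participant, who is the mother. No section settles the matter, so staff could decide differently from case to case.
2. **Is the infant asked about as a safety matter?** The focus in 8.2.4 does not mention the infant. Section 1.3 has a single post-baseline visit, so there is one scheduled safety inquiry after randomization.
3. **Is there a listed risk?** Section 2.3.1 has none for the sleep component and none for the infant under intervention-related risks.
4. **Are infant data used for safety?** The two questionnaires are collected twice in both arms. Sections 8.2, 8.3, 9.3 and 9.4 give them no safety table, no threshold for review and no link to event reporting. Section 8.1 lists no infant growth, injury or illness item.
5. **Are the routes equal between arms?** Study visits are common to both. The coach belongs to Sleep GOALS (Sections 2.3.2, 4.1 and 6.2), while controls receive brochures.

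**What 20 infants per arm could show.** Section 9.2 gives 40 participants, 20 per group. Section 5.1 requires a singleton pregnancy, hence one infant per mother. The 16 per arm below is 20 less the 20% loss that the benchmark in Section 3 tolerates: 20 × 0.80 = 16.

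One-sided 95% upper limit after zero events in n: 1 − 0.05^(1/n).
- n = 16: 17.1%
- n = 20: 13.9%
- n = 40: 7.2%

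Chance of at least one event in n at true rate p: 1 − (1 − p)^n. The documents give no infant event rate, so the values of p are assumptions, and every event is taken to be recorded.

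| p | n = 20 | n = 40 |
|---|---|---|
| 1% | 18% | 33% |
| 2% | 33% | 55% |
| 5% | 64% | 87% |
| 10% | 88% | 99% |

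These figures show the resolution of the proposed question. They do not measure the gap in the plan.

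**The case against.** A reader might infer that infant harm could not be detected in either arm, that 40 infants go unobserved, or that the data would exclude nothing. The documents do not support this.

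- Infant sleep and feeding are measured at baseline and Week 16 in both arms, so a shift in either could be seen.
- The definition of an unanticipated problem in Section 8.3.1 includes the criterion "Suggests that the research places participants or others at a greater risk of harm", so an infant event can be reported by that route.
- Section 10.1.2.1 has the PI review data bi-monthly, including for safety issues, and does not confine that review to logged adverse events.
- The text in 8.2.4 states a focus, not a limit, and does not say whose sleep or diet is meant. That it covers only the mother is a fair inference, not a statement in the plan.

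A reader might also infer that expectedness cannot be judged without an infant entry in the risk list. It can. Section 8.2.3.3 calls an event unexpected if it "is not consistent with the risk information previously described for the study intervention", so an unlisted infant event is simply unexpected, which helps it qualify under 8.3.1.

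Nor is infant sleep shown to be a direct target. Section 5 speaks of strategies for maternal sleep, infant sleep is one coaching example, and no procedure applied to the infant is described. Finally, this is a 40-person pilot without formal testing, and no primary endpoint or weight estimate is affected.

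All of this limits the point without removing it. The unanticipated-problem route handles events already known and requires them to be unexpected, related or possibly related, and suggestive of greater risk; it does not find them. The bi-monthly review is general. The questionnaires have no stated safety use.

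**Conclusion.** The point holds as a gap in systematic ascertainment. Infant events are not defined as a safety outcome, no standard infant safety question is planned, the infant questionnaires have no stated safety use, and one named reporting route exists in one arm only. It does not show that harm would be missed, and it identifies no specific harm.

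The consequence is confined to what the pilot can say about safety and what it passes to the larger trial. The size of the unequal ascertainment cannot be computed, because the documents give neither an event rate nor a reporting rate. Even with complete ascertainment the evidence would be weak: zero events among 20 infants in an arm remains compatible with a true rate of up to about 14%.

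The conclusion assumes that some enrolled mothers breastfeed or take up infant sleep with the coach, which the plan permits but does not quantify. Consent pages were not available, so nothing is concluded about whether the consent form mentions the infant. This is a cheap improvement worth making, not a fault in the design of the main comparison.

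**What to change.** - **Section 8.2.4:** state that infant events are recorded. At the Week 16 visit, ask one identical question in both arms: any feeding, growth, sleep-related or other medical problem in the infant since baseline.
- **Event log:** record the source of each report and keep coach-reported events separate, so that the comparison between arms rests on the common question.
- **Section 9.4:** tabulate the existing infant sleep and feeding questionnaires by arm, at baseline and Week 16, as descriptive safety data without testing.
- **Section 2.3.1:** add the sleep component and the infant to the intervention-related risks.

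The cost is a slightly longer existing visit, one more field in the log, one table and an IRB amendment. No new visit or questionnaire is needed. The report should say plainly that 20 infants per arm support description only.

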8.2.5 ADVERSE EVENT REPORTING

The investigator must record nonserious adverse events and report them to the sponsor within 24-hours of the PI learning about the event.

8.2.6 SERIOUS ADVERSE EVENT REPORTING

The PI will immediately report to the sponsor any serious adverse event, whether or not considered study intervention related, including those listed in the protocol, and must include an assessment of whether there is a reasonable possibility that the study intervention caused the event. Study endpoints that are serious adverse events (e.g., all-cause mortality) must be reported in accordance with the protocol unless there is evidence suggesting a causal relationship between the study intervention and the event. In that case, the investigator must immediately report the event to the sponsor.

All serious adverse events (SAEs) will be followed until satisfactory resolution or until the site investigator deems the event to be chronic or the participant is stable. Other supporting documentation of the event may be requested by the study sponsor and should be provided as soon as possible.

8.2.7 REPORTING EVENTS TO PARTICIPANTS

We will inform participants of adverse events (AEs) that are related to the safety and welfare of the participants. To inform participants, we will take the following steps:

1. Assess the relevance and impact of the AE: Evaluate the AE to determine whether it has any direct implications for the participants' safety, welfare, or rights. If the AE is deemed relevant and important to the participants, proceed with informing them.
2. Update the informed consent document: If the AE warrants a change to the study protocol, intervention, or the risks and benefits associated with participation, revise the informed consent document accordingly. Any changes must be approved by the Institutional Review Board (IRB) before sharing the updated document with participants.
3. Prepare clear and concise communication: Develop a written or verbal communication that clearly explains the nature of the AE, its potential impact on participants, and any changes to the study protocol, procedures, or risks. Use plain language that is easily understood by the target audience and avoid jargon or technical terms.
4. Choose an appropriate communication method: Depending on the nature and urgency of the AE, select an appropriate method to inform participants. This could include individual meetings, phone calls, emails, or letters. In some cases, a combination of methods may be necessary to ensure all participants are informed promptly.
5. Provide an opportunity for questions and discussion: Allow participants the opportunity to ask questions, discuss their concerns, and seek clarification about the UP and its implications. This can be done during individual meetings, phone calls, or through written correspondence (e.g., email).
6. Re-obtain informed consent, if necessary: If the AE has led to significant changes in the study protocol or risks, you may need to re-obtain informed consent from participants. Provide them with the updated, informed consent document, discuss the changes, and obtain their signature if they agree to continue participating in the study.
7. Document the process: Keep a record of the steps taken to inform participants about the AE, including the date of communication, the method used, and any feedback or concerns raised by the participants. This documentation will be important for monitoring purposes and to demonstrate compliance with ethical guidelines and regulations.

8.3 UNANTICIPATED PROBLEMS

8.3.1 DEFINITION OF UNANTICIPATED PROBLEMS (UP)

The Office for Human Research Protections (OHRP) considers unanticipated problems involving risks to participants or others to include, in general, any incident, experience, or outcome that meets **all** of the following criteria:

- Unexpected in terms of nature, severity, or frequency given (a) the research procedures that are described in the protocol-related documents, such as the Institutional Review Board (IRB)-approved research protocol and informed consent document; and (b) the characteristics of the participant population being studied;
- Related or possibly related to participation in the research (“possibly related” means there is a reasonable possibility that the incident, experience, or outcome may have been caused by the procedures involved in the research); and
- Suggests that the research places participants or others at a greater risk of harm (including physical, psychological, economic, or social harm) than was previously known or recognized.

8.3.2 UNANTICIPATED PROBLEM REPORTING

The investigator will report unanticipated problems (UPs) to the reviewing Institutional Review Board (IRB) and principal investigator (PI). The UP report will include the following information:

- Protocol identifying information: protocol title and number, PI's name, and the IRB project number;
- A detailed description of the event, incident, experience, or outcome;
- An explanation of the basis for determining that the event, incident, experience, or outcome represents a UP;
- A description of any changes to the protocol or other corrective actions that have been taken or are proposed in response to the UP.

UPs will be reported using the following timeline to satisfy the requirement for prompt reporting:

- UPs that are serious adverse events (SAEs) will be reported to the IRB and study sponsor within 48 hours of the investigator becoming aware of the event.
- Any other UP will be reported to the IRB and sponsor within 5 business days of the investigator becoming aware of the problem.
- All UPs should be reported to appropriate institutional officials (as required by an institution's written reporting procedures), the supporting agency head (or designee), and the Office for Human Research Protections (OHRP) within 5 business days of the IRB's receipt of the report of the problem from the investigator.]

8.3.3 REPORTING UNANTICIPATED PROBLEMS TO PARTICIPANTS

We will inform participants of unanticipated problems (UPs) that are related to the safety and welfare of the participants. To inform participants, we will take the following steps:

1. Assess the relevance and impact of the UP: Evaluate the UP to determine whether it has any direct implications for the participants' safety, welfare, or rights. If the UP is deemed relevant and important to the participants, proceed with informing them.
2. Update the informed consent document: If the UP warrants a change to the study protocol, intervention, or the risks and benefits associated with participation, revise the informed consent document accordingly. Any changes must be approved by the Institutional Review Board (IRB) before sharing the updated document with participants.
3. Prepare clear and concise communication: Develop a written or verbal communication that clearly explains the nature of the UP, its potential impact on participants, and any changes to the study protocol, procedures, or risks. Use plain language that is easily understood by the target audience and avoid jargon or technical terms.
4. Choose an appropriate communication method: Depending on the nature and urgency of the UP, select an appropriate method to inform participants. This could include individual meetings, phone calls, emails, or letters. In some cases, a combination of methods may be necessary to ensure all participants are informed promptly.
5. Provide an opportunity for questions and discussion: Allow participants the opportunity to ask questions, discuss their concerns, and seek clarification about the UP and its implications. This can be done during individual meetings, phone calls, or through written correspondence (e.g., email).
6. Re-obtain informed consent, if necessary: If the UP has led to significant changes in the study protocol or risks, you may need to re-obtain informed consent from participants. Provide them with the updated, informed consent document, discuss the changes, and obtain their signature if they agree to continue participating in the study.

7. Document the process: Keep a record of the steps taken to inform participants about the UP, including the date of communication, the method used, and any feedback or concerns raised by the participants. This documentation will be important for monitoring purposes and to demonstrate compliance with ethical guidelines and regulations.

